7.1 Inclusion Criteria

Patients eligible for the trial must comply with all of the following at baseline:

- 1. A diagnosis of CRPS I or II according to the Budapest research criteria at the time of assessment for this study.
- 2. First documented diagnosis of Budapest CRPS by a healthcare professional not less than 18 months and not longer than 15 years before the screening assessment. A valid documented diagnosis must either include the term 'Budapest CRPS', or must include the term 'CRPS' and in addition documentation of the presence of signs and symptoms which allow making the Budapest diagnosis from the notes.
- 3. Pain intensity average 6 or greater on a 0-10 point numerical rating scale (NRS) over a minimum of seven consecutive daily entries prior to baseline (0 day) visit, with no single value below 5.
- 4. Completed a previous course of appropriate specialised physiotherapy.
- 5. Poor response or intolerance to at least one anti-neuropathic pain medication such as tricyclic antidepressants or gabapentinoids.
- 6. If a woman of childbearing potential (WOCBP), to be willing to confirm the use of adequate birth control during the trial period unless pregnancy is impossible
- 7. Fertile male patients to be using contraception for the duration of therapy if sexually active with a female partner
- 8. Age 18 years and over.
- 9. Written and informed consent obtained from patient and agreement of patient to comply with the requirements of the study.

Please refer to section 7.4 for contraception and pregnancy testing in relation to Inclusion criteria 6 and 7

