A daily diary will be given to each participant to record pain intensity scores over seven consecutive days prior to their baseline (0 day) visit. This score is a self-measurement pain intensity NRS with 0 as no pain and 10 as the worst pain possible. A mean pain intensity of 6 on a 0-10 point NRS over the seven consecutive daily entries prior to their baseline (0 day) visit is required for eligibility. The pain intensity must not have been less than 5 on any single day. Participants will be encouraged to complete the diary on each day around the same time. They are advised to not complete the diary in retrospect. After screening, participants will be contacted by telephone once, between 1 and 3 days prior to the baseline visit to check pain diary scores. The implications of taking Anakinra abroad (e.g. possible increased travel insurance premiums etc) will be discussed with the participant. Patients will be advised that Anakinra may not be stored outside of the fridge for periods of up to 12 hours, it should be stored at an appropriate temperature (between 2°C and 8°C) using a cool bag.

If participants are not eligible at any point they will not be rescreened, unless the reason for non-eligibility is short term and has been resolved in the opinion of the investigator. Participants who are found to be ineligible during the screening visit or during the telephone call to check diary scores will not need to attend for the baseline visit. The baseline visit should be arranged during the screening visit.

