10.4 Registration/Baseline visit (Day 0, visit 1)

Eligibility can only be confirmed by CI or PI or their delegate. Eligibility assessment must not occur until fully informed consent is documented. Eligibility criteria are described in detail in Section 7.

Eligibility confirmation must be documented in the participant's medical notes and then on the trial's Eligibility CRF. Details must include at a minimum who confirmed full eligibility, when this was confirmed, and when the participant was formally entered into the trial.

Eligibility will be confirmed in two stages, i) from information obtained at the screening visit, ii) from the results of pain diaries completed between screening visit and registration visit, and results of screening blood tests, and TB screening where appropriate.

Baseline assessments should be completed as per the Schedule of Assessments (Section 10.7) in order to accurately complete the Baseline CRF and collect the necessary information for the trial analyses. This includes the following assessments:

- Vital signs
- Pain Intensity on a 0-10 NRS with 0 being no pain and 10 being the worst pain experienced, over the past 24hr.
- CRPS Severity score
- PHQ-9
- EQ-5D-5L
- HADS
- BPI
- Mechanical QST this will be completed twice for the purposes of the sub study: once blindfolded and once non-blindfolded with the order decided at random (see section 10.4.1)
- Work status
- Medication use in opioid (Morphine) equivalents

10.4.1 **Sub study Randomisation**

During the baseline visit, participants will be randomised to inform the order in which the baseline mechanical QST assessment should be performed. Randomisation will be via a secure (24-hour) web-based randomisation system controlled centrally by the LCTC. A personal login username and password, provided

by the LCTC, will be required to access the randomisation system; designated research staff will be issued with their personal login and password upon completion of training in the use of the system.

When the system requirements are confirmed, a unique randomisation number will be displayed on a secure webpage along with the allocated sequence for the QST to be completed in. An automated email confirmation will be sent to the authorised randomiser. Note that the randomisation number will not be required as a participant identifier for the purposes of the trial as the randomisation relates to the sub study only.

Randomisation: web access https://ctrc.liv.ac.uk/Randomisation/INCA

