#### 25.1.2.4 Futility

The average CRPS pain over the 2 weeks prior to visit 5 (day 120) will be calculated using the Pain diaries days 106 to 119 whereby the average will be:

[the sum of the completed days 106 to 119]/ [number of completed entries].

The baseline pain score, ranging from 0 to 10, is collected on Form 4: Baseline as the average pain from CRPS over the last 24 hours. The average difference will be calculated as the average pain over the 2 weeks prior to visit 5 – baseline measure (day 0). The difference will then be classified for each participant as  $\geq$  2 points of pain reduction on the NRS (rounded to the nearest whole number) or less than 2 points of pain reduction on the NRS, including an increase in score.

After 12 participants have been recruited and completed 4 months treatment period the criteria is met if both of the below are met:

- An average of no pain increase among the completed patients
- At least one participant reporting at least 2 points of pain reduction on the NRS

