#### 25.2.3.2.1.1 Derivation

The total weekly score will be calculated as the total NRS score per week for days 93 to 120 (last 4 weeks, inclusive of days 93 and 120) from the patient pain diaries. The mean of the total weekly scores (average weekly score) per patient will be calculated as:

[sum of total weekly scores for days 93 to 120 (inclusive)]/ 4.

The mean daily average over the last month per patient will be calculated as:

[sum of the scores for days 93 to 120 (inclusive)]/28.

The change in score will be the weekly and daily average at day 120 minus the baseline score. The baseline score is collected on Form 4: Baseline and is the average pain from CRPS over the last 24 hours at baseline.

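### The pain change subtracts one 24-hour baseline rating from a 28-day or 14-day diary mean, leaving the required pre-treatment diary unused and adding avoidable noise to the SD and the futility check

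*SAP*

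**What the plan says.** **Final analysis (SAP 25.2.3.2.1.1).** The day-120 daily average is "sum of the scores for days 93 to 120 (inclusive)]/28", taken from the pain diaries. The change is that average minus baseline, and the baseline is defined as follows: "The baseline score is collected on Form 4: Baseline and is the average pain from CRPS over the last 24 hours at baseline".

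**Futility criterion (SAP 25.1.2.4).** End-of-treatment pain "will be calculated using the Pain diaries days 106 to 119". The baseline it is compared with "is collected on Form 4: Baseline as the average pain from CRPS over the last 24 hours".

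**Pre-treatment diary.** Protocol 7.1, criterion 3, requires mean pain of at least 6 "over a minimum of seven consecutive daily entries prior to baseline (0 day) visit, with no single value below 5". Protocol 10.3 issues a diary for up to two weeks for this purpose. In the SAP this diary appears only as a category of ineligibility (19.1).

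**Use of the result.** Protocol 14.2 names pain change as the main outcome contributing data to later studies and says it will inform the next sample size. SAP 25.2.3.2.1.2 summarises the change by mean and SD, among other statistics.

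**Scale wording.** On the screening diary, Protocol 10.3 says: "This score is a self-measurement pain intensity NRS with 0 as no pain and 10 as the worst pain possible". For the baseline visit, Protocol 10.4 lists: "Pain Intensity on a 0-10 NRS with 0 being no pain and 10 being the worst pain experienced, over the past 24hr".

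**The concern.** The two ends of the change differ in kind. One is a single rating covering 24 hours, recorded on a visit form. The other averages 14 or 28 diary entries. Pain varies from day to day. A 28-day mean removes most of that variation, while a single rating carries all of it into the change.

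Two uses are exposed. A planner who takes the SD of change from this study would carry baseline noise into the next sample size. The futility check asks whether at least one of 12 completers improved by 2 points, which is a question about the most extreme individual and so is sensitive to noise in single values. The matching pre-treatment measure already exists for every eligible participant.

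**Working it through.** **No plan figure to reproduce.** The sample size of 30 rests on cited rules of thumb (Protocol 14.2). The documents give no SD of pain change and no day-to-day SD, so both are assumed below and varied.

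**Inputs.** Days averaged at baseline: m_b = 1 (planned) or 7 (diary). Days averaged at the end: m_f = 28 (final analysis) or 14 (futility). Assumed: day-to-day SD σ = 0.5 to 1.5; SD of true individual change τ = 1 to 2; day-to-day autocorrelation ρ = 0 or 0.5. The clinic rating is taken to vary like one diary day.

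**Formula (independent days).** Var(change) = τ² + σ²/m_b + σ²/m_f. With autocorrelation, each σ²/m is multiplied by 1 + 2Σ(1 − k/m)ρ^k. With independent days, the excess variance from using one rating is σ²(1 − 1/7) = 0.857σ².

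**Middle case, τ = 1.5, σ = 1, m_f = 28.**
- Single rating: √(2.25 + 1 + 1/28) = √3.286 = 1.81.
- Seven-day diary: √(2.25 + 1/7 + 1/28) = √2.429 = 1.56.
- Variance ratio: 3.286/2.429 = 1.35.

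For illustration, a two-arm trial with an assumed 1-point difference, 90% power and two-sided 5% needs 2(1.960 + 1.282)² × Var per arm. That is 70 against 52.

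| τ = 1.5, independent days | SD, single rating | SD, 7-day diary | Variance ratio | n per arm |
|---|---|---|---|---|
| σ = 0.5 | 1.58 | 1.51 | 1.09 | 53 vs 49 |
| σ = 1.0 | 1.81 | 1.56 | 1.35 | 70 vs 52 |
| σ = 1.5 | 2.14 | 1.63 | 1.73 | 97 vs 56 |

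**Full grid with the eligibility rule.** Simulated integer scores, limited to 0-10, were selected on a 7-day mean of at least 6 with no day below 5. Over all τ, σ and ρ above, the variance ratio ran from 1.07 to 2.56. The single rating gave the larger SD in every scenario.

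**Futility, individual limb.** A reduction that rounds to 2 points is one of 1.5 or more. Suppose nobody truly changes. With σ = 1 and a single rating, the SD of the observed difference is √(1 + 1/14) = 1.035. The chance per person is Φ(−1.5/1.035) = 0.074, and for at least one of 12 it is 1 − 0.926¹² = 0.60. With the diary the SD is √(1/7 + 1/14) = 0.463 and the chance for 12 is below 1%. Simulation with integer scores and the eligibility rule gives:

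| Limb passed by noise alone | Single rating | 7-day diary |
|---|---|---|
| σ = 0.5 | about 7% | 0% |
| σ = 1.0 | about 64% | about 1% |
| σ = 1.5 | about 89% | about 26% |

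**Cost of the diary baseline.** The diary is also what selects participants, so later values tend to drift down from it. The extra shift towards apparent benefit was about 0.02 to 0.18 points. With no true change, the limb requiring that mean pain has not risen passed about 51% of the time with the single rating and 61% to 83% with the diary.

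**The case against.** - **A baseline separate from the selection diary is defensible.** In an uncontrolled study, regression to the mean looks like benefit, and the single rating suffers less from it. This stands. It is why the Form 4 change should be kept alongside and why the average-change limb should be shown both ways.
- **Like-for-like comparisons already exist.** The CRPS severity form (SAP 25.2.3.2.2) and the BPI pain items (25.2.3.2.7) are collected at baseline and day 120, and end-of-treatment pain is also summarised on its own. True, but none of these is the change that Protocol 14.2 singles out, and none repairs the futility calculation.
- **The stakes are limited.** This is a secondary outcome with no formal test, and Protocol 11 calls the progression criteria a guide. With 30 participants, a 95% interval for any SD already runs from about 0.80 to 1.34 times the estimate. That limits the urgency. It does not justify adding avoidable noise.
- **An anchor mismatch.** A reader might infer from Protocol 10.3 and 10.4 that the baseline and the day 93-120 diary use different top anchors, so that every participant's change is shifted the same way. The documents do not support this. The wording in 10.3 describes the screening diary, the anchors of the diary given after registration are not stated, and the forms are not included.

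**Conclusion.** The point holds for averaging period and setting. The direction is secure whenever pain varies from day to day: the planned SD of change exceeds that of a diary-to-diary change. The size is not fixed by the documents. Under the assumed ranges the variance is roughly 1.1 to 2.6 times as large. At a day-to-day SD near 0.5 the excess is small in most scenarios, and at 1.5 it is substantial.

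A reader might take the 35% to 73% excess at τ = 1.5 and σ = 1.0 to 1.5 as the amount by which the next trial would be oversized. That is too firm. It fixes one true-change SD and a narrow noise range, and it presumes that the next trial would use a diary baseline and analyse change scores, which the documents do not say.

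The consequence for futility is clearer. At a day-to-day SD of 1 or more, the individual-reduction limb is passed more often than not with no true change in anyone. The primary safety outcome is unaffected.

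**What to change.** 1. In SAP 25.2.3.2.1.1 and Table 25-1, define baseline pain for the change outcome as the mean of the seven daily diary entries before day 0. Report the change from the Form 4 rating alongside as a sensitivity analysis.
2. In SAP 25.1.2.4, use the diary baseline for the individual 2-point limb. Show the IDSMC the average-change limb with both baselines, with a note on regression to the mean.
3. Check the scale anchors on Form 4, the screening diary and the post-registration diary, and record the result.
4. Apply the new baseline to the daily average. The SAP's weekly score is a mean of seven-day totals (0-70). Constant pain of 7 would give 49 − 7 = +42, so that scale needs its own correction.

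The cost is SAP wording and entry of the screening diary values if they are not already in the database. A short protocol clarification may be needed if baseline (day 0) is read as the visit rating only. No new visits or participant burden follow. The price is the regression to the mean described above, which reporting both baselines makes visible.

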#### 25.2.3.2.1.2 Analysis

Continuous data will be summarised using mean, SD, median, IQR, maximum and minimum value. Summaries will be provided for:

- Baseline score
- Average weekly scores (days 93 to 120)
- Daily average over the last month (days 93 to 120)
- Change in scores for weekly and daily average at day 120 from baseline.

#### 25.2.3.2.2 CRPS severity score

#### 25.2.3.2.2.1 Derivation

The CRPS Severity score CRF collects the NRS pain score now and over the last 24 hours. The change in score will be calculated as the score at day 120 minus baseline score.

#### 25.2.3.2.2. Analysis

Continuous data will be summarised as in Section 25.2.3.2.1.2. Summaries will be provided for:

- Baseline score
- Day 120 score
- Change from baseline.

Continuous summaries will also be provided for scores at day 30, 60 and 90. Profile plots will also be provided from baseline to day 120.

#### 25.2.3.2.3 Global assessment of change

#### 25.2.3.2.3.1 Derivation

Global assessment of change is collected at day 120 on the Patient Global Impression of Change form. Patients are asked the following question "How would you describe your overall status regarding your pain since starting treatment?", which has the following answers:

- Very much improved
- Much improved
- Minimal Improvement
- No change
- Minimally worse
- Much worse
- Very much worse

#### 25.2.3.2.3.2 Analysis

The number of patients to complete the form will be reported. Categorical data will be summarised using frequencies and percentages at day 120 with the denominator being those who completed the question.

#### 25.2.3.2.4 Analgesic Medication use

#### 25.2.3.2.4.1 Derivation

Analgesic medication use is collected throughout the trial on the concomitant medications form and is indicated from the variable "Type of medication". Patients taking Analgesic medications as recorded on the Concomitant medications form as a start date on or before registration (and end date post-registration) will be classified as taking Analgesic medications at baseline. At day 120 patients with an 'ongoing' end date or end date after day 120 (start date pre-day 120) for Analgesic medications on the Concomitant medications form will be classified as taking Analgesic medications at day 120. Analgesic medication use at day 180 will be defined similarly with day 180 replacing day 120.

A patient will also be classified as prescribed Analgesic medications throughout the trial if any Analgesic medication has a start date between registration and day 120, this will also be summarised from registration to day 180.

LCTC\_ST003\_TEMP1: SAP Template, V0.1, 08/01/2021 (developed using LCTC\_GE001\_TEMP4: LCTC Template of a Template, V1.0, 04/09/2020)

CLINICAL TRIALS CENTRE LCTC

25.2.3.2.4.2 Analysis

Categorical data for analgesic medication use will be summarised using frequencies and percentages

at baseline and day 120 with the denominator as the number of patients registered and the number

to reach day 120 (defined as attended Visit 5 Form 6 day 120). A summary of Analgesic medications

prescribed throughout the trial will also be provided by the number of events (courses) and the

number of patients. The percentage of patients to be prescribed the analgesic medication will be

calculated using the denominator of the number of patients registered.

To compare analgesic medication use at baseline and day 120 a cross-tabulation will be provided with

two percentages using the denominators of total number of patients in the category at baseline and

day 120 i.e. row and column percentages.

Analgesic medication use at day 180 will be summarised in line with the above with day 180 replacing

day 120.

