Participants are free to withdraw from follow up at any time without providing a reason, though a reason should be recorded if one is given. Those who wish to withdraw from further follow-up will have the data collected up to the point of that withdrawal included in the analyses. The participant will not contribute further data to the study unless this is required by law (e.g. safety events).

The LCTC should be notified of withdrawals from the study as soon as possible, a completed Withdrawal from Study CRF must be returned to the LCTC within 7 days.

In situations where study withdrawal is due to an AE, participants will be followed up until resolution of that AE or determination that the participant's condition is stable.

In case of premature discontinuation, the participant will be assessed for AEs, if any, and medication use.

Participant Transfer

If a patient moves from the area, every effort should be made for the patient to continue in the trial if they are happy to travel to site from their new location. If they are no longer able to continue with study visits (and therefore study treatment) every effort should be made by the site to follow up the patient as far as is possible. The trial provides financial support to participants of travel expenses of up to £20 per visit.

Loss to Follow-up

A participant will be considered lost to follow up if s/he fails to return for 2 scheduled visits and is not contactable by the site research team.

If a participant fails to attend/facilitate a required study visit the following actions must be taken:

- Site will attempt to contact the participant and reschedule the missed visit and advise the participant on the importance of maintaining the assigned visit schedule.
- Before a participant is deemed to be lost to follow up, site research staff will make every effort to regain contact with the participant (i.e. 3 telephone calls and, if necessary, a headed letter to last known address). These efforts should be recorded in the participants medical notes.
- If the participant continues to be unreachable they should be considered withdrawn from the study with a primary reason of lost to follow up and this should be recorded on the appropriate CRF.

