#### 22 Analysis Datasets

#### 22.1 Efficacy Analyses

The primary and secondary outcome analyses will be conducted on all registered participants and for whom the outcome(s) of interest have been observed/measured. Patients who withdrew consent for trial continuation will contribute outcome data up until the point of withdrawal unless the patients' specifically request that the data are not to be used. No imputations will be made.

The membership of the analysis set for each outcome will be determined and documented and reasons for participant exclusion will be given prior to analysis. Reasons may include missing data, loss to follow up.

A per protocol analysis will not be performed, instead the occurrence of each protocol deviation will be monitored and sensitivity analysis performed as appropriate with patients experiencing deviations

of concern removed. The sensitivity analysis will apply to a secondary analysis of the primary outcome only.

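### SAP 25.2.3.2.4 counts analgesic users at day 120 and day 180 from open records without requiring that the participant was still in follow-up, but divides the day-120 count by Visit 5 attendees

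*SAP*

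**What the plan says.** The derivation (SAP 25.2.3.2.4.1) works from the concomitant medications form. For the later time point it reads "At day 120 patients with an 'ongoing' end date or end date after day 120 (start date pre-day 120) for Analgesic medications", and such patients are classified as taking analgesics at day 120. Nothing in it requires attendance or continued follow-up. The rule is then extended: "Analgesic medication use at day 180 will be defined similarly with day 180 replacing day 120".

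The analysis (SAP 25.2.3.2.4.2) reports frequencies and percentages. The baseline denominator is the number registered. The day-120 denominator is the number "to reach day 120 (defined as attended Visit 5 Form 6 day 120". A baseline by day-120 cross-tabulation follows, with "two percentages using the denominators of total number of patients in the category at baseline and" at day 120, that is, row and column percentages. It carries no attendance condition either.

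SAP 22.1 sets a general rule for primary and secondary outcomes. The analysis covers registered participants "for whom the outcome(s) of interest have been observed/measured". It adds: "Patients who withdrew consent for trial continuation will contribute outcome data up until the point of withdrawal", unless they ask for their data not to be used. It rules out imputation and names loss to follow-up as a possible reason for exclusion. SAP 25.2.3.2.4 neither repeats this rule nor refers to it.

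**The concern.** The numerator and the denominator of the day-120 percentage are defined on different groups of people. The numerator takes anyone with an open record; the denominator takes those who came to Visit 5.

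Open records for early leavers are plausible. Protocol 10.9 asks for medication use to be assessed when a participant withdraws, and the schedule in Protocol 10.7 has concomitant medication reviewed at premature discontinuation. After withdrawal from follow-up, "The participant will not contribute further data to the study unless this is required by law (e.g. safety events"). A participant lost to follow-up cannot be contacted. A drug still being taken at the last contact may therefore never receive an end date. Taken literally, the derivation turns that last status into use at day 120, and again at day 180. In effect this carries the last value forward.

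Analgesic use is one of the outcomes collected to help design the randomised trial. In a single-arm study it also helps a reader interpret a change in pain. With 30 participants, a few misplaced people move the percentage noticeably.

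**Working it through.** The documents state no analgesic-use figure, so there is nothing to reproduce. The check is direct arithmetic on the stated rule.

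**Inputs**
- Planned number registered: 30 (SAP 16; Protocol 14.2).
- A = participants who attended Visit 5. Assumed 27 or 24, so 3 or 6 leavers.
- U = analgesic users among the attendees. Assumed 60% to 100% of A.
- L = non-attendees whose record is still marked ongoing. Assumed 50% to 100% of leavers, in whole persons: 2 to 3 of 3 (1.5 rounded up to 2), and 3 to 6 of 6.

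The documents give none of A, U or L.

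**Formulas**
- Literal rule: (U + L)/A.
- Numerator limited to the denominator's population: U/A.
- Excess: (U + L)/A − U/A = L/A. It does not depend on U and is never negative.
- The literal rule passes 100% when U + L > A, that is, when L > A − U.

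**Results**

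| A | Leavers | L | U | Literal (U + L)/A | Matched U/A | Excess L/A (points) |
|---|---|---|---|---|---|---|
| 27 | 3 | 2 | 22 | 24/27 = 88.9% | 22/27 = 81.5% | 7.4 |
| 27 | 3 | 3 | 22 | 25/27 = 92.6% | 22/27 = 81.5% | 11.1 |
| 24 | 6 | 3 | 19 | 22/24 = 91.7% | 19/24 = 79.2% | 12.5 |
| 24 | 6 | 5 | 22 | 27/24 = 112.5% | 22/24 = 91.7% | 20.8 |
| 24 | 6 | 6 | 19 | 25/24 = 104.2% | 19/24 = 79.2% | 25.0 |

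**When 100% is passed**
- A = 27, L = 3: at most 2 attendees may be non-users, so U is at least 25 (25/27 = 92.6%).
- A = 24, L = 3: again at most 2 non-users, so U is at least 22 (22/24 = 91.7%).
- A = 24, L = 6: at most 5 non-users, so U is at least 19 (19/24 = 79.2%).

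**When there is no effect.** If SAP 22.1 is applied to the numerator, or if no non-attendee has an open record, L = 0 and the two rules agree.

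**Cross-tabulation.** Its percentages are of row and column totals, so they cannot exceed 100%. A leaver with an open record at both points would still appear as a continuing user without having been observed at day 120. A leaver whose analgesic ended before exit would appear as a non-user, also unobserved.

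**Comparison with other outcomes.** For global assessment of change (SAP 25.2.3.2.3.2) and work status (SAP 25.2.3.2.11.2) the denominator is those who answered the question, so the mismatch does not arise.

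**The case against.** The strongest reply is that SAP 22.1 already settles the matter. A participant who left at day 40 has no observed day-120 status, contributes only up to withdrawal, and may be excluded for loss to follow-up. A percentage of those who reached day 120 is also most naturally a count of users among them. On that reading L = 0.

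This shows the likely intent, but it does not clearly override the specific derivation. The ongoing entry is itself data collected before withdrawal, so SAP 22.1 keeps it. The derivation then turns it into a non-missing day-120 value, so nothing is flagged as missing. Loss to follow-up is listed only as a reason that may apply. Two programmers could follow the SAP and obtain different results.

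Other parts of the reply stand:
- How open records are closed at exit depends on the medication form and the data management plan, which are not among the documents.
- Participants who stop anakinra but stay in follow-up attend Visit 5 and are counted correctly.
- Someone who misses Visit 5 but is reached at day 180 may be a genuine day-120 user who is missing from the denominator. Strict restriction to Visit 5 attendees would lose that person.

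A reader might also combine the rule with the 50% treatment-completion threshold in Protocol 11 and infer percentages well above 100%. The documents do not support this. The threshold concerns completing active treatment, and Protocol 10.9 expects those who stop treatment to continue their visits.

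**Conclusion.** The SAP is internally inconsistent here. Its specific rule, read literally, counts unobserved participants as users, while its general rule points to leaving them out. Under the literal rule the frequency-table percentage is too high by L/A: about 7 to 11 percentage points with 3 leavers of 30 and 12.5 to 25 with 6. These figures rest on assumed attendance and on 50% to 100% of leavers having an open record. Passing 100% is possible but needs L to exceed the number of attendees not using analgesics.

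Three stronger readings are tempting and do not hold:
- *Use will be overstated.* This is conditional on the literal reading and on L being above zero.
- *The bias always runs towards no reduction in use.* The upward direction is secure for the frequency table only. In the cross-tabulation it depends on how leavers compare with attendees.
- *Any analgesic-sparing effect is hidden.* The any-use indicator cannot show a dose reduction, whoever is counted.

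Importance is minor to moderate. This is a descriptive secondary outcome, it is not a progression criterion (Protocol 11), and sample size for the next study rests on pain intensity (Protocol 14.2).

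**What to change.** In SAP 25.2.3.2.4.1, state that analgesic status is derived only for participants whose medication was reviewed at or after the time point: Visit 5 or a later contact for day 120, and telephone follow-up 5 for day 180. Define this by visit rather than calendar day, because Protocol 10.7 allows 3 days either side.

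In SAP 25.2.3.2.4.2, use that same set as the denominator and for the matching cross-tabulations, report all other registered participants as not assessed, and refer to SAP 22.1. Name the day-180 denominator explicitly, since the day-120 one is tied to the Visit 5 form.

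The percentage then cannot exceed 100%. If none of the non-attendees is reviewed later, the fourth row of the table changes from 112.5% to 91.7%. Someone who misses Visit 5 but is reviewed at day 180 enters both numerator (if a user) and denominator. The cost is a sentence or two in the SAP and one program condition, with no new data.
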